1. VERSION HISTORY

Table 1. Summary of Changes

Version/ Date	Associated Protocol Amendment	Rationale	Specific Changes
1 02 May 2023	Original 22 Apr 2023	N/A	N/A
2 23 June 2023	Original 22 Apr 2023	
 Included Guillain-Barre syndrome, atrial fibrillation, and polyneuropathy as Tier 1 events for RSVpreF per CBER request; provided additional information on Tier 2 and Tier 3 events. Clarified the AESI analysis is for the protocol-specified AESIs. Typo correction. 	
 Added the rationale and/or definition of Tier 1, Tier 2 and Tier 3 events in Section 3.5.1; added the analysis of Tier 1 events and the description of the 3-tier approach in Section 6.6.1. Added “protocol-specified” to AESIs in Section 3.1.2.3. Deleted “(the combination group and the sequential-administration group)” in Section 5.2.2.3.
3 01 August 2023	Original 22 Apr 2023	
 Updated reactogenicity analysis based on CBER feedback for other vaccine program studies. 	
 Updated to include both related and unrelated AEs within 7 days after vaccination for pooling with reactogenicity data in Section 3.1.2. Added e-diary completion to Section 3.4.3 and the details in Section 6.5.1. Clarified the applicable analysis for “safety population” and added “e-diary safety population” in Section 4. Clarified the handling of missing e-diary data in Section 5.3.1.1. In Section 6.1.3 and Section 6.1.4, clarified analysis of local reactions and systemic events and added sensitivity analyses for reactogenicity maximum severity and AE summary.

Table 1. Summary of Changes

Version/ Date	Associated Protocol Amendment	Rationale	Specific Changes
		
2. Updated immunogenicity analysis based on CBER feedback to RSV studies and the clinical development plan on combined vaccine.
 
3. Clarified the derivation for cases of myocarditis or pericarditis.
 
4. Updated the meaning of “N-binding antibody” at baseline.
 
5. Typo correction.
	
2. Added seroresponse for RSV A and RSV B in Section 3.3.6 and its analysis in Section 6.3.4. Added a descriptive immunogenicity analysis for combining Groups 1 and 2 in Section 6.3.5.3.
 
3. Updated Section 3.5.3.
 
4. Updated Section 3.4.2.
 
5. Changed “GMR of NTs” to “GMR of HAI titers” in the secondary immunogenicity objective on QIV (Group 7 versus Group 5) in the Section 2.2 table, and changed “these assessment” to “these assessments” in Section 3.5.3.

2. INTRODUCTION

This SAP provides the detailed methodology for summary and statistical analyses of the data collected in Study C5481001 – Substudy A.

This document may modify the plans outlined in the protocol; however, any major modifications of the primary endpoint definition or its analysis will also be reflected in a protocol amendment.

2.1. Modifications to the Analysis Plan Described in the Protocol

There is no change in analysis from the plan specified in the protocol.

2.2. Study Objectives, Endpoints, and Estimands

Type	Objectives	Estimands	Endpoints
Primary Safety	To describe the safety and tolerability of [RSVpreF+BNT162b2]	
In participants receiving study intervention, the percentage of participants reporting:
 
 Local reactions within 7 days following vaccination Systemic events within 7 days following vaccination AEs from vaccination through 1 month after vaccination SAEs from vaccination through 6 months after vaccination 	
 Local reactions (pain at the injection site, redness, and swelling) Systemic events (fever, fatigue, headache, chills, vomiting, diarrhea, new or worsened muscle pain, and new or worsened joint pain) AEs SAEs
Primary Immunogenicity	
To demonstrate that the immune responses elicited by [RSVpreF+BNT162b2] when coadministered with QIV are noninferior to those elicited by each vaccine alone:
 
 RSVpreF alone (Group 1 vs Group 4) Bivalent BNT162b2 alone (Group 1 vs Group 3) QIV alone (Group 1 vs Group 5) 	
 In participants in compliance with the key protocol criteria (evaluable participants for Groups 1 and 4): 
 GMR of NTs at 1 month after vaccination in Group 1 to Group 4 for RSV subgroup A GMR of NTs at 1 month after vaccination in Group 1 to Group 4 for RSV subgroup B In participants in compliance with the key protocol criteria (evaluable participants for Groups 1 and 3): 
 GMR of NTs at 1 month after vaccination in Group 1 to Group 3 for SARS-CoV-2 Omicron BA.4/BA.5 GMR of NTs at 1 month after vaccination in Group 1 to Group 3 for SARS-CoV-2 reference strain BA.4/BA.5 In participants in compliance with the key protocol criteria (evaluable participants for Groups 1 and 5): 
 GMR of HAI titers at 1 month after vaccination in Group 1 to Group 5 for each influenza strain included in QIV 	
 RSV A and RSV B NTs SARS-CoV-2 Omicron BA.4/BA.5 and reference-strain NTs HAI titers for each strain contained in the QIV

Type	Objectives	Estimands	Endpoints
Primary Immunogenicity	To demonstrate that the immune responses elicited by [RSVpreF+BNT162b2] are noninferior to those elicited by each vaccine alone: 
 1. RSVpreF alone (Group 2 vs Group 4) 2. Bivalent BNT162b2 alone (Group 2 vs Group 3) 	
 1. In participants in compliance with the key protocol criteria (evaluable participants for Groups 2 and 4): 
 • GMR of NTs at 1 month after vaccination in Group 2 to Group 4 for RSV subgroup A • GMR of NTs at 1 month after vaccination in Group 2 to Group 4 for RSV subgroup B 2. In participants in compliance with the key protocol criteria (evaluable participants for Groups 2 and 3): 
 • GMR of NTs at 1 month after vaccination in Group 2 to Group 3 for SARS-CoV-2 Omicron BA.4/BA.5 • GMR of NTs at 1 month after vaccination in Group 2 to Group 3 for SARS-CoV-2 reference strain 	
 1. RSV A and RSV B NTs 2. SARS-CoV-2 Omicron BA.4/BA.5 and reference-strain NTs
Secondary Immunogenicity	To demonstrate that the immune responses elicited by RSVpreF, bivalent BNT162b2, and QIV, when administered concomitantly, are noninferior to those elicited by each vaccine alone: 
 1. RSVpreF (Group 7 vs Group 4) 2. Bivalent BNT162b2 (Group 7 vs Group 3) 3. QIV (Group 7 vs Group 5) 	
 1. In participants in compliance with the key protocol criteria (evaluable participants for Groups 7 and 4): 
 • GMR of NTs at 1 month after vaccination in Group 7 to Group 4 for RSV subgroup A • GMR of NTs at 1 month after vaccination in Group 7 to Group 4 for RSV subgroup B 2. In participants in compliance with the key protocol criteria (evaluable participants for Groups 7 and 3): 
 • GMR of NTs at 1 month after vaccination in Group 7 to Group 3 for SARS-CoV-2 Omicron BA.4/BA.5 • GMR of NTs at 1 month after vaccination in Group 7 to Group 3 for SARS-CoV-2 reference strain 3. In participants in compliance with the key protocol criteria (evaluable participants for Groups 7 and 5): 
 • GMR of HAI titers at 1 month after vaccination in Group 7 to Group 5 for each influenza strain included in the QIV 	
 1. RSV A and RSV B NTs 2. SARS-CoV-2 Omicron BA.4/BA.5 and reference-strain NTs 3. HAI titers for each strain contained in the QIV

Type	Objectives	Estimands	Endpoints
Secondary Immunogenicity	To demonstrate that the immune responses elicited by RSVpreF and bivalent BNT162b2 when administered concomitantly are noninferior to those elicited by each vaccine alone: 
 1. RSVpreF (Group 6 vs Group 4) 2. Bivalent BNT162b2 (Group 6 vs Group 3) 	
 1. In participants in compliance with the key protocol criteria (evaluable participants for Groups 6 and 4): 
 • GMR of NTs at 1 month after vaccination in Group 6 to Group 4 for RSV subgroup A • GMR of NTs at 1 month after vaccination in Group 6 to Group 4 for RSV subgroup B 2. In participants in compliance with the key protocol criteria (evaluable participants for Groups 6 and 3): 
 • GMR of NTs at 1 month after vaccination in Group 6 to Group 3 for SARS-CoV-2 Omicron BA.4/BA.5 • GMR of NTs at 1 month after vaccination in Group 6 to Group 3 for SARS-CoV-2 reference strain 	
 1. RSV A and RSV B NTs 2. SARS-CoV-2 Omicron BA.4/BA.5 and reference-strain NTs
Exploratory	To further describe the immune responses elicited by [RSVpreF+BNT162b2]	
 • N/A 	
 • N/A

2.2.1. Primary Estimands

2.2.1.1. Primary Immunogenicity Estimands for Combination Vaccine Coadministration With QIV Noninferiority Objective

The primary estimands for the first primary immunogenicity objective will use the hypothetical strategy to estimate the immune response difference elicited from Group 1, compared with Groups 3, 4, and 5, respectively. In other words, the immune response is estimated in the hypothetical setting where participants follow the vaccines administered and protocol requirements as directed. It includes the following 5 attributes:

- **Treatment condition:** Randomized to Group 1, 3, 4, or 5.
- **Population:** Participants as defined by the study inclusion/exclusion criteria for Substudy A.
- **Variables:** Each of the following serology results measured at Visit A102:
 - RSV subgroup A NT
 - RSV subgroup B NT
 - SARS-CoV-2 Omicron BA.4/BA.5 NT

- SARS-CoV-2 reference-strain NT
- Influenza A (H1N1) HAI titer
- Influenza A (H3N2) HAI titer
- Influenza B1 (Victoria) HAI titer
- Influenza B2 (Yamagata) HAI titer
- **Intercurrent events:** The following intercurrent events could impact the interpretation or the measurement of the immune response:
 1. The participant did not receive the vaccine as randomized (participants who were randomized to Group 1 should have received both [RSVpreF+BNT162b2] and QIV; participants who were randomized to Group 4 should have received RSVpreF; participants who were randomized to Group 3 should have received BNT162b2; and participants who were randomized to Group 5 should have received QIV).
 2. The participant did not meet the inclusion criteria or did meet the exclusion criteria.
 3. Major protocol violations: The participant received a prohibited vaccine or treatment that may alter the immune response from the vaccination and blood draw visit.
 4. Blood was taken outside the window of 27 to 42 days after vaccination for immunogenicity evaluation.

The clinical question of interest is based on whether immune response elicited by [RSVpreF+BNT162b2], when coadministered with QIV, without any influence from any other immune-modifying drugs or vaccines and measured within a homogeneous time window, is noninferior to that elicited by RSVpreF, BNT162b2, and QIV alone. Therefore, all data after intercurrent events 1, 2, and 3, as well as all data at intercurrent event 4, if collected, will be excluded. Major protocol violations will be determined by clinical review.

- **Population-level summary:** GMR, defined as the ratio of each applicable variable GMT, between Group 1 and Groups 3, 4, and 5, respectively.

2.2.1.2. Primary Immunogenicity Estimands for Combination Vaccine Noninferiority Objective

The primary estimands for the second primary immunogenicity objective will use the hypothetical strategy to estimate the immune response difference elicited from Group 2, compared with Group 3 and Group 4, respectively. In other words, the immune response is estimated in the hypothetical setting where participants follow the vaccines administered and protocol requirements as directed. It includes the following 5 attributes:

- **Treatment condition:** Randomized to Group 2, 3, or 4.

- **Population:** Participants as defined by the study inclusion/exclusion criteria for Study C5481001 – Substudy A.
- **Variables:** Each of the following serology results measured at Visit A102:
 - RSV subgroup A NT
 - RSV subgroup B NT
 - SARS-CoV-2 Omicron BA.4/BA.5 NT
 - SARS-CoV-2 reference-strain NT
- **Intercurrent events:** The following intercurrent events could impact the interpretation or the measurement of the immune response:
 1. The participant did not receive the vaccine as randomized (participants who were randomized to Group 2 should have received [RSVpreF+BNT162b2]; participants who were randomized to Group 4 should have received RSVpreF; and participants who were randomized to Group 3 should have received BNT162b2).
 2. The participant did not meet the inclusion criteria or did meet the exclusion criteria.
 3. Major protocol violations: The participant received a prohibited vaccine or treatment that may alter the immune response from the vaccination and blood draw visit.
 4. Blood was taken outside the window of 27 to 42 days after vaccination for immunogenicity evaluation.

The clinical question of interest is based on whether immune response elicited from [RSVpreF+BNT162b2], without any influence from any other immune-modifying drugs or vaccines and measured within a homogeneous time window, is noninferior to that elicited from RSVpreF and BNT162b2 alone. Therefore, all data after intercurrent events 1, 2, and 3, as well as all data at intercurrent event 4, if collected, will be excluded. Major protocol violations will be determined by clinical review.

- **Population-level summary:** GMR, defined as the ratio of each applicable variable GMT, between Group 2 and Groups 3 and 4, respectively.

2.2.1.3. Primary Safety Estimands

2.2.1.3.1. Reactogenicity Estimands

The primary estimands for the safety objective will use the treatment policy strategy and estimate the safety rate, regardless of whether an intercurrent event occurs.

Reactogenicity estimands have the following 5 attributes:

- **Treatment condition:** [RSVpreF+BNT162b2] coadministered with QIV, [RSVpreF+BNT162b2], BNT162b2, RSVpreF, QIV, RSVpreF coadministered with BNT162b2, and RSVpreF coadministered with BNT162b2 and QIV.
- **Population:** Participants as defined by the study inclusion/exclusion criteria for Substudy A.
- **Variables:** Each item included in the e-diary reported from Days 1 through 7 after vaccination (refer to [Section 3.1.2.1](#) and [Section 3.1.2.2](#)).
- **Intercurrent events:** All data collected after the intercurrent event will be included.
- **Population-level summary:** The rates of variables (each reported reactogenicity item) in each treatment condition.

2.2.1.3.2. AE Estimands

AE estimands have the same attributes (treatment condition, population, intercurrent events) as reactogenicity estimands ([Section 2.2.1.3.1](#)), except:

- **Variables:** Any AEs reported within 1 month after vaccination ([Section 3.1.2.3](#)).
- **Population-level summary:** The rates of the variable (any AE reported within 1 month after vaccination) in each treatment condition.

2.2.1.3.3. SAE Estimands

SAE estimands have the same attributes (treatment condition, population, intercurrent events, population-level summary) as AE estimands ([Section 2.2.1.3.2](#)), except:

- **Variables:** Any SAEs reported throughout 6 months after vaccination ([Section 3.1.2.3](#)).

2.2.2. Secondary Estimands

2.2.2.1. Secondary Immunogenicity Estimands for 3-Vaccine Coadministration Noninferiority Objective

The estimand attributes are the same as the first primary immunogenicity estimand ([Section 2.2.1.1](#)), except:

- **Treatment condition**: Randomized to Group 7, 3, 4, or 5.
- **Intercurrent events**: Participants who were randomized to Group 7 should have received all 3 individual vaccines: RSVpreF, BNT162b2, and QIV.
- **Population-level summary**: GMR, defined as the ratio of each applicable variable GMT, between Group 7 and Groups 3, 4, and 5, respectively.

2.2.2.2. Secondary Immunogenicity Estimands for RSVpreF and BNT162b2 Coadministration Noninferiority Objective

The estimand attributes are the same as the second primary immunogenicity estimand ([Section 2.2.1.2](#)), except:

- **Treatment condition**: Randomized to Groups 6, 3, and 4.
- **Intercurrent events**: Participants who were randomized to Group 6 should have received both individual vaccines: RSVpreF and BNT162b2.
Participants who were randomized to Group 6 should have received 2 individual vaccines: RSVpreF and BNT162b2.
- **Population-level summary**: GMR, defined as the ratio of each applicable variable GMT, between Group 6 and Groups 3 and 4, respectively.

2.2.3. Additional Estimands

Additional estimands, as supplementary analyses to support the primary and secondary immunogenicity objectives, are defined. The table below lists the variables and strategies for addressing intercurrent events, which are listed in [Sections 2.2.1.1](#), [2.2.1.2](#), and 2.2.2 for the immunogenicity objectives. The remaining 4 estimand attributes (treatment condition, variables, population, and population-level summary) are the same for each objective.

Objective	Intercurrent Events Handling Strategy
Primary combination vaccine coadministration with QIV noninferiority	Treatment policy
Primary combination vaccine noninferiority	Treatment policy
Secondary 3-vaccine coadministration noninferiority	Treatment policy
Secondary RSVpreF and BNT162b2 coadministration noninferiority	Treatment policy

2.3. Study Design

This is a Phase 1/2 randomized, parallel-group, observer-blinded substudy to assess the safety, tolerability, and immunogenicity of a combined RSVpreF and bivalent BNT162b2 (original/Omi BA.4/BA.5) vaccine, [RSVpreF+BNT162b2], administered concomitantly with a seasonal influenza vaccine or administered alone. Approximately 1050 healthy participants ≥ 65 years of age will be enrolled and randomized to 7 groups across 2 strata, as illustrated below.

All participants will be asked to complete a reactogenicity e-diary for 7 days following vaccination. AEs and SAEs will be collected from the signing of informed consent through Visit A102 (1-month follow-up visit). SAEs will be collected from the signing of informed consent through Visit A103 (6-month telephone contact).

Blood samples will be collected for immunogenicity assessments prior to vaccination at Visit A101 and 1 month after vaccination (Visit A102). Immunogenicity measured by HAI titers for the matched seasonal strains ($2\times A$, $2\times B$) recommended by WHO will be assessed for Groups 1, 5, and 7; immunogenicity measured by SARS-CoV-2 neutralization assay (both reference strain and Omicron BA.4/BA.5) will be assessed for Groups 1, 2, 3, 6, and 7; and immunogenicity measured by RSV A and RSV B serum NTs will be assessed for Groups 1, 2, 4, 6, and 7.

	Vaccination			1-Month Follow-Up Visit	6-Month Telephone Contact
Approximate Month (Visit Window)	0 (Day 1)			1 (28 to 35 Days After Vaccination)	6 (175 to 189 Days After Vaccination)
Visit Identifier	Visit A101			Visit A102	Visit A103
	Vaccination 1 (Right Arm)		Vaccination 2 (Left Arm)	Vaccination 3 (Right Arm)	
Group 1 (n=150)	 Combination [RSVpreF+BNT162b2]	QIV			
Group 2 (n=150)	 Combination [RSVpreF+BNT162b2]	Placebo			
Group 3 (n=150)	 Bivalent BNT162b2	Placebo			
Group 4 (n=150)	 RSVpreF	Placebo			
Group 5 (n=150)	 QIV	Placebo			
Group 6 ^a (n=150)	 Bivalent BNT162b2	Placebo	RSVpreF		
Group 7 ^a (n=150)	 Bivalent BNT162b2	QIV	RSVpreF		
 Blood collection  Telephone contact					

a. Separate administration sites on right arm by 1 inch (2.5 cm).

3. ENDPOINTS AND BASELINE VARIABLES: DEFINITIONS AND CONVENTIONS

3.1. Primary Endpoints

3.1.1. Primary Immunogenicity Endpoints

Immunogenicity measured by HAI titers for the matched seasonal strains (2×A, 2×B) recommended by WHO will be assessed for Groups 1, 5, and 7; immunogenicity measured by SARS-CoV-2 neutralization assay (both reference strain and Omicron BA.4/BA.5) will be assessed for Groups 1, 2, 3, 6, and 7; and immunogenicity measured by RSV A and RSV B serum NTs will be assessed for Groups 1, 2, 4, 6, and 7. An unblinded statistician will send the barcode listings to sample management for specific assay testing.

Only the immunogenicity results measured at the Month 1 visit from each applicable group are relevant to the primary endpoint.

Titers above the LLOQ are considered accurate and their quantitated values will be reported. Refer to [Section 5.3.2](#) for LLOQ details. Titers below the corresponding LLOQ, denoted as BLQ, will be set to $0.5 \times \text{LLOQ}$ for analysis. Missing assay results will not be imputed.

3.1.2. Primary Safety Endpoints

Primary safety endpoints include both reactogenicity data and AEs collected from the e-diary and AE CRF.

Based on feedback from FDA on multiple vaccine programs, reactogenicity data will utilize both e-diary data (prompted local reactions and systemic events) and reactogenicity events reported in the AE CRF during the e-diary collection period. Since the AE CRF does not designate a specific page to collect reactogenicity data for an untransmitted e-diary, Pfizer has adopted a process of providing a listing of AEs reported within 7 days after vaccination to the clinical team to review and determine (“flag”) which PTs should be considered reactogenicity events before the database lock. AEs reported on the same day of vaccination but missing a start time are defaulted to AEs reported after vaccination. Following these review steps, those AEs reported within 7 days after vaccination that match flagged PTs will be considered as reactogenicity data. If the same reactogenicity event is reported on the same day from both the e-diary and the AE CRF, the highest grade from the 2 data sources will be used for that specific day for analysis.

It should be noted that the data collection in the AE CRF is different from that of the e-diary:

- For redness, swelling, and fever, the measured size of redness and swelling at the injection site and temperature are recorded in the e-diary, but not in the AE CRF. As the missing e-diary entries are monitored with ongoing review of the prompted reactions reported in the AE CRF, any measurement recorded in the query response will be taken into consideration for the primary analysis, using the data handling memo for analysis purposes. For the 7 days, only the maximum grading from both sources will be used for the aggregated severity analysis.

- For pain at the injection site and all other systemic events, the severity grading algorithm for the e-diary data and the AE CRF may not be the same. Pfizer will choose the highest severity grade.

If a participant did not have any e-diary data transferred within 7 days after vaccination, the AE CRF data will not be used for derivation, because doing so may inflate the denominator and bias the analysis, since participants who did not transfer e-diary data may be less likely to report reactogenicity data. If a participant did not report any e-diary data, the participant will not be included in the analysis of reactogenicity data.

The subsections below describe how to derive each safety endpoint.

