3.1.2.3. Adverse Events and Serious Adverse Events

Standard algorithms for handling missing AE dates and missing AE severity levels will be applied as described in the Pfizer vaccine data standard rules. Completely missing AE start dates will not be imputed.

The following derivations (yes/no) will be included for each participant:

1. Any AE reported through 1 month after vaccination: If the AE started on the same day of vaccination, and the AE start time is before the vaccination time, then this AE will not be counted. Otherwise, if the AE start time is missing or after the vaccination time, the AE will be included.
2. Any related AE reported through 1 month after vaccination: This is similar to the above except only the related AE is included (excluding the related reactogenicity reported within 7 days after vaccination [[Section 3.1.2](#)]).
3. Any immediate AE (AE start time is within 30 minutes after vaccination) reported after vaccination: Only include AEs that started on the same day of vaccination and with a nonmissing AE start time that is within 30 minutes of vaccination. If the immediate AE is a related reactogenicity event, it would not be included as an immediate AE.
4. Any severe or life-threatening AE reported through 1 month after vaccination.
5. Any AE leading to study withdrawal after vaccination.
6. Any AE leading to death after vaccination.
7. Any SAE reported from vaccination throughout the substudy (including reactogenicity reported in the AE CRF during the e-diary collection period).
8. Any protocol-specified AESI reported from vaccination throughout the substudy. The following are protocol-specified AESIs based on AE PTs:
 - Confirmed diagnosis of influenza.
 - Confirmed diagnosis of RSV infection.
 - Confirmed diagnosis of myocarditis or pericarditis occurring within 4 weeks after vaccination. See PTs provided in [Section 3.5.3](#).
 - Confirmed COVID-19 diagnosis after Visit 1 through the end of the study (clinical signs/symptoms per [CDC¹](#) and positive SARS-CoV-2 NAAT or rapid antigen test result).

Variables 1 through 6 listed above will be derived with 2 approaches: excluding any reactogenicity (but not excluding reactogenicity SAEs) reported in the AE CRF during the e-diary collection period, and with no exclusion at all.

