4. ANALYSIS SETS (POPULATIONS FOR ANALYSIS)

Data for all participants will be assessed to determine if participants meet the criteria for inclusion in each analysis population prior to unblinding and releasing the database and classifications will be documented per standard operating procedures.

For purposes of analysis, the following analysis sets are defined:

Participant Analysis Set	Description	Applicable Analysis
Enrolled	All participants who sign the ICD.	Study conduct such as participant disposition
Randomized population	All participants who are assigned a randomization number in the IWRS regardless of whether or not the study intervention was administered.	Immunogenicity analysis population disposition
Safety population	All participants who receive the study intervention.	AE/SAE analysis

Participant Analysis Set	Description	Applicable Analysis
E-diary safety population	All participants who receive the study intervention with at least 1 day of e-diary data transmitted. Note: if all participants have at least 1 day of e-diary data transmitted, this will be the same as the safety population.	Local reactions and systemic events analysis
ITT immunogenicity population	All randomized participants who receive the study intervention and have at least 1 valid and determinate assay result after vaccination.	Supplementary analysis on primary/secondary immunogenicity endpoints
Evaluable immunogenicity population	All participants randomized in Substudy A who meet the following criteria: 
 • Are eligible for this substudy. • Received study intervention(s) to which they were randomized. • Had the 1-month postvaccination blood collection within 27 to 42 days after vaccination. • Had no major protocol violations from vaccination randomization through the 1-month postvaccination blood draw. • Had at least 1 valid and determinate assay result 1 month after vaccination. 	Primary analysis population for immunogenicity endpoints (primary/secondary/exploratory)

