5.3.1.1. Reactogenicity Data

For derived variables based on the reactogenicity data, if any day of the 7-day e-diary is available, the “any day (Days 1-7)” data will be considered nonmissing.

The reactogenicity data are mostly collected through the e-diary, which does not allow participants to skip the question. Therefore, for a specific day, if the e-diary data are transferred for that day, all of the reactogenicity data for the participant on that day are nonmissing.

In general, for any participant with all 7 days of the e-diary data missing, this participant will not be included in the analysis (ie, assuming MCAR). If only 1 to 6 days of e-diary data are transferred, it is expected that these reactogenicity events would be queried by the investigator for the missing e-diary days and entered in the AE CRF if any reactogenicity was not reported in the e-diary due to missed days. Therefore, the primary analysis will use reactogenicity recorded in the AE CRF to impute the partially missed e-diary data to estimate the reactogenicity rate during the e-diary collection period. The AE CRF is designed as a log page, which means only events that occurred will be recorded and events that did not occur will not be recorded. Therefore, all remaining missing days are considered as “no.” This imputation can reasonably estimate the reactogenicity event rates during the e-diary collection period. However, data for the missing day(s) will not be imputed in the analysis of each specific day.

A sensitivity analysis will be planned for participants who completed the e-diary. Only participants with all 7 days of e-diary transferred data will be included in this sensitivity analysis.

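### Two small gaps in the safety derivations: flagged nonserious AEs in participants with no e-diary reach neither main table on a literal reading, and CRF local reactions are pooled without an arm condition

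*SAP*

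**What the plan says.** **Which CRF events become reactogenicity.** SAP 3.1.2 has the clinical team review a pre-lock listing and flag preferred terms; then "those AEs reported within 7 days after vaccination that match flagged PTs will be considered as reactogenicity data". The sentence sets no condition on diary status or on arm. SAP 3.1.2.1 carries these events into the local reaction derivations.

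**Participants with no e-diary.** The same section says that for them "the AE CRF data will not be used for derivation, because doing so may inflate the denominator". SAP 5.3.1.1 agrees: "for any participant with all 7 days of the e-diary data missing, this participant will not be included in the analysis". The e-diary safety population in SAP 4 is defined as "All participants who receive the study intervention with at least 1 day of e-diary data transmitted".

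**The AE tables.** SAP 3.1.2.3 derives variables 1 to 6 in two ways: "excluding any reactogenicity (but not excluding reactogenicity SAEs) reported in the AE CRF during the e-diary collection period", "and with no exclusion at all". Two variables also carry an exclusion in their own definitions. Related AEs are counted "excluding the related reactogenicity reported within 7 days after vaccination", with a cross-reference to SAP 3.1.2. For immediate AEs: "If the immediate AE is a related reactogenicity event, it would not be included as an immediate AE". SAP 6.1.4.1 makes the version with the exclusion (SAEs retained) the main analysis, on the safety population. SAP 6.1.4.3 adds a sensitivity analysis on all AEs.

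**Arms.** Protocol 8.3.4.2 has participants assess local reactions on the right arm. In the schema (protocol 10.11.2), every group also receives a left-arm injection: QIV in Groups 1 and 7, placebo in Groups 2 to 6.

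**The concern.** Taking reactogenicity out of the main AE table makes sense when the reactogenicity table counts the same event. For a participant with no diary it does not, and the AE CRF is then the only record. The participant stays in the AE denominator while a flagged nonserious event leaves the numerator, so the main AE percentage can be slightly too low.

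The arm question concerns the other table. Reactions recorded in the diary need not be entered as AEs (protocol 8.3.4), but a left-arm reaction has no diary field, so the CRF is its only recording route. If it is pooled, one percentage combines right-arm diary data with CRF data from either arm. Any carry-over could differ between groups, because the left arm holds an active vaccine only in Groups 1 and 7. Grade 4 local reactions come only from the CRF (SAP 3.1.2.1.2, Table 4, note b), so that category has no arm restriction at all. A pooled left-arm event also drops out of the main AE table.

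AEs and local reactions are primary safety endpoints, so their main tables should follow one unambiguous rule.

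**Working it through.** The plan states no figure on this point, so there is none to reproduce. The check applies the written rules to every type of AE within 7 days of vaccination.

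**Step 1. Rules.**
- Reactogenicity table: counted if at least 1 e-diary day was transmitted and the term is flagged (SAP 3.1.2, 4, 5.3.1.1).
- Main AE table: counted if the term is not flagged, or the event is an SAE (SAP 3.1.2.3, 6.1.4.1).
- All-AE sensitivity analysis: always counted (SAP 6.1.4.3).

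**Step 2. The eight combinations.**

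| Any e-diary | Flagged term | Serious | Reactogenicity table | Main AE table | All-AE analysis |
|---|---|---|---|---|---|
| yes | yes | yes | yes | yes | yes |
| yes | yes | no | yes | no | yes |
| yes | no | yes | no | yes | yes |
| yes | no | no | no | yes | yes |
| no | yes | yes | no | yes | yes |
| **no** | **yes** | **no** | **no** | **no** | **yes** |
| no | no | yes | no | yes | yes |
| no | no | no | no | yes | yes |

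Exactly one combination reaches neither main table: no diary, flagged term, nonserious. It is still reported in the no-exclusion derivations of variables 1 to 6 and in the all-AE analysis. It is also in the individual-AE summaries of SAP 6.6.1, so far as those follow the no-exclusion derivations.

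**Step 3. Arm condition.** The pooling rule in SAP 3.1.2 and 3.1.2.1 uses two criteria, preferred term and the 7-day window. Neither section adds a third criterion for the arm. SAP 3.1.2 mentions a data handling memo for measurements obtained by query; it is not among the documents, nor is the CRF.

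**Step 4. Size per participant.** The planned group size is 150 (protocol 10.11.11.5). One participant is 1/150 = 0.67 percentage points; two are 2/150 = 1.33; three are 3/150 = 2.00.
- For the AE table, this applies to a participant with no other AE that already counts in the any-AE rate.
- For local reactions, it applies to a participant whose only pooled reaction is on the left arm.

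For scale, the planned Clopper-Pearson 95% interval is 5.7% to 16.0% for 15/150 and 41.7% to 58.3% for 75/150, so the half-widths are about 5.1 and 8.3 points.

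**Step 5. What cannot be computed.** The number of affected participants depends on the no-diary rate, the share of those participants with a flagged CRF event, and the share of CRF local reactions on the left arm. The documents give none of these, so no total is offered.

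**The case against.** **The events may revert to ordinary AEs.** The related-AE variable refers back to SAP 3.1.2, which says CRF data are not used for derivation when there is no diary. On that reading no reactogenicity event exists for such a participant, and the exclusion has nothing to remove. This is possible, but no sentence says it, and the rule that flagged events are reactogenicity data carries no diary condition. Two competent programmers could produce different main tables.

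**The events are reported anyway.** This stands. A reader might infer that they vanish from the study report. They do not: the no-exclusion derivations and the all-AE analysis include them, and SAEs are in the main table as well. What the all-AE analysis cannot do is isolate them, because it restores flagged events for everyone.

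**A departure from the protocol.** A reader might infer a conflict with protocol 10.11.11.3.2, which calls for all AEs through 1 month to be summarised, given that SAP 2.1 declares no change. The documents do not support this as a point about no-diary participants. The all-AE analysis meets the requirement, and if the main-table exclusion were a departure, it would be one for every participant.

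**Left-arm events may already be screened out.** A reader might infer that left-arm reactions do contaminate the local reaction rates. That is not shown. SAP 3.1.2 describes ongoing review of the prompted reactions, which are right-arm reactions, and an arm check could sit in the review or in the memo. The e-diary-only analysis and its difference from the primary one (SAP 6.1.3.3) also show the whole CRF contribution, which bounds any carry-over, although not by arm. What stands is that the SAP states no arm condition.

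**Conclusion.** Both points hold as minor gaps in the written rules. The first follows directly from the text on a literal reading; the alternative reading is open but unstated. The second is a possibility that the rules permit, not a demonstrated error. Both affect descriptive safety percentages only: no hypothesis test is touched and SAEs are kept.

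The total size of either effect cannot be derived from the documents. The only firm figure is 0.67 points per affected participant, assuming the planned 150 per group. The first effect can only lower the main AE rate. In the second, a pooled left-arm event can raise the local reaction rate and is also missing from the main AE table. A handful of participants would stay well inside the confidence intervals already planned, so this is a matter of clear definition rather than a threat to the safety conclusions.

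**What to change.** **(1) AE exclusion.** In SAP 3.1.2.3, including the related-AE and immediate-AE definitions, and in SAP 6.1.4.1, apply the reactogenicity exclusion only to participants in the e-diary safety population. Add a footnote to the main AE table giving, by group, the number of no-diary participants whose flagged events are counted. Keep the all-AE sensitivity analysis.

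Cost: a sentence in each section, one population condition in programming and one footnote. The downside is that the main AE percentage then counts reactogenicity terms for no-diary participants only, so it depends slightly on diary compliance. The footnote discloses this. If the sponsor already intends these events to remain AEs, the same sentence records it.

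**(2) Arm condition.** In SAP 3.1.2, add to the pre-lock listing review that a CRF local reaction placed on the left arm by the record or a query is not pooled and stays in the main AE analysis. Keep arm-unknown events pooled as now, and report their number by group. Moving them out could undo the pooling that the SAP adopted on FDA feedback.

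Cost: an arm check on a listing that is reviewed anyway. If the CRF does not record the arm, flagged injection-site events would need a site query. No new visits are required.
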